9.4.5 Safety analyses

Safety data will not be formally analyzed but appropriate summaries for safety data will be produced, as defined below. All patients who received at least 1 dose of study drug will be included in the assessment of the safety profile (safety analysis set).

Data from all cycles of initial treatment will be presented as described in the Statistical Analysis Plan. Adverse events will be listed individually by patient and dose group. For

patients who have a dose modification, all AEs (due to drug or otherwise) will be assigned to the initial dose group. The number of patients experiencing each AE will be summarized by the Medical Dictionary for Regulatory Activities (MedDRA) system organ class, MedDRA preferred term, and CTCAE grade. The number and percentage of patients with AEs in different categories (e.g., causally related, CTCAE Grade ≥ 3 , etc.) will be summarized by dose group, and events in each category will be further summarized by MedDRA system organ class and preferred term, by dose group. Serious AEs will be summarized separately if a sufficient number occur.

Any AE occurring before the first dose of IP (i.e., before study Day 1) will be included in the data listings, but will not be included in the summary tables of AEs.

Any AE occurring within the defined follow-up period (see modules for specific time period) after discontinuation of IP will be included in the AE summaries. Any AEs in this period that occur after a patient has received further therapy for cancer (following discontinuation of IP) will be flagged in the data listings. Adverse events occurring after the 30-day or 90-day follow-up period after discontinuation of IP will be listed separately, but not included in the summaries.

Hematology, clinical chemistry, vital signs, ECG data, ECHO/MUGA, demographic data, medical histories, and concomitant medications will be listed individually by patient and suitably summarized. For all laboratory variables, which are included in the current version of CTCAE, the CTCAE grade will be calculated. Summary statistics of mean, median, standard deviation, minimum, maximum and number of observations will be used.

Details of any deaths will be listed for all patients.

Graphical presentations of safety data will be presented as is deemed appropriate. This may include, but is not restricted to, presentation of parameters against time, concentration or shift plots. Appropriate scatter plots will also be considered to investigate trends in parameters compared to baseline.

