7.1.1 Procedures for discontinuation of study treatment

The Investigator should instruct the patient to contact the site before or at the time if study treatment is stopped. Discontinuation of study treatment, for any reason, does not impact the patient's participation in the study. A patient that decides to discontinue study treatment will always be asked about the reason(s) and the presence of any AEs. The date of last intake of study treatment and the combinational agent should be documented in the eCRF. All study treatment should be returned by the patient at his next on-site study visit or unscheduled visit. Patients permanently discontinuing study treatment should be given locally available standard of care therapy, at the discretion of the Investigator.

The patient should continue attending subsequent study visits and data collection should continue according to the study protocol. If the patient does not agree to continue in-person study visits, a modified follow-up must be arranged to ensure the collection of endpoints and safety information. This could be a telephone contact with the patient, a contact with a relative or treating physician, and/or information from medical records. The approach taken should be recorded in the medical records. A patient who agrees to modified follow-up is not considered to have withdrawn consent or to have withdrawn from the study.

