8.3.4 Adverse event data collection

The following variables will be collected for each AE:

- AE (verbatim)

- The date when the AE started and stopped
- CTCAE grade/maximum CTCAE grade
- Whether the AE is serious or not
- Investigator causality rating against the IP(s) (yes or no)
- Action taken with regard to IP(s)
- Action taken with regard to procedure or concomitant medication
- Outcome
- Does the Investigator consider this AE an ImAE?

In addition, the following variables will be collected for SAEs:

- Date AE met criteria for serious AE
- Date Investigator became aware of serious AE
- AE is serious due to which criterion
- Date of hospitalization
- Date of discharge
- Probable cause of death
- Date of death
- Autopsy performed
- Causality assessment in relation to study procedure(s)
- Causality assessment in relation to other medication

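### The all-cause AE summaries in Section 9.4.5 include events that start after further cancer therapy, with no table that separates them

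*Protocol*

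**What the plan says.** Section 9.4.5 states the inclusion rule directly: "Any AE occurring within the defined follow-up period (see modules for specific time period) after discontinuation of IP will be included in the AE summaries". It then turns to events in that period with onset after further cancer therapy (the two sentences meet at "will be included in the AE summaries. Any AEs in this period that occur after a patient has received further therapy for cancer"), and its only provision is that these, "following discontinuation of IP) will be flagged in the data listings". It names two exclusions from the summaries. One is events before the first dose. The other is late events: "Adverse events occurring after the 30-day or 90-day follow-up period after discontinuation of IP will be listed separately, but not included in the summaries". The start of a new anticancer therapy is not a cut-off, and no other part of the protocol text at hand tabulates these events apart.

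Two further provisions bear on the point. Section 7.1.1 says: "Patients permanently discontinuing study treatment should be given locally available standard of care therapy, at the discretion of the Investigator". On causality, Section 8.3.4 collects for each AE an "Investigator causality rating against the IP(s) (yes or no"), and Section 9.4.5 uses it as one of its summary categories: "The number and percentage of patients with AEs in different categories (e.g., causally related, CTCAE Grade" 3 or higher, and so on).

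**The concern.** Each module is a single-arm cohort of approximately 30 patients (Section 1.1), intended to identify treatments to take forward (Section 9.2). Safety and tolerability of each regimen is a stated objective (Section 3) and part of the primary aim (Section 9). With no control arm, the AE tables are read at face value as the profile of the regimen.

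If an event begins after the patient has started another cancer drug, an all-cause table counts it in the study regimen's incidence. The flag that would show this is only in the listings, so a reader of the tables cannot tell how many events are of this kind. With 30 patients, each such patient moves a rate by 1/30, or about 3.3 percentage points.

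**Working it through.** The plan gives no figure on this point to reproduce. The check has two parts: which tables the rule reaches, and how far a rate could move.

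**Which tables.** Read together, the provisions of 9.4.5 leave three periods:

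- Before first dose: listed, not summarised.
- First dose to the end of the 30- or 90-day window: summarised, whether or not new therapy has begun. Onset after new therapy is flagged in the listings only.
- After the window: listed separately, not summarised.

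The tables by system organ class, preferred term and CTCAE grade, the Grade 3 or higher category and the serious AE summary (produced if numbers allow) do not depend on cause, so they can take in next-line events. The same section shows the all-cause approach for dose groups: for "patients who have a dose modification, all AEs (due to drug or otherwise) will be assigned to the initial dose group". The causally related category differs. An event enters it only if the investigator answers yes for the study product (Sections 8.3.4 and 8.3.5).

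**How far a rate could move.** Inputs:

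- n = 30 patients per module (Section 1.1).
- a = proportion with a given AE category before any new therapy. Not in the protocol; assumed 20-40%.
- f = proportion starting new therapy inside the window. Not in the protocol; assumed 10-50%.
- b = proportion of those with an event of that category after starting it, inside the window. Not in the protocol; assumed 10-50%.

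Treating the two sources as independent, the tabulated rate is 1 - (1 - a)(1 - f × b). The excess over a is (1 - a) × f × b, and the extra patients are n times that.

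| a | f | b | Tabulated rate | Extra patients of 30 |
|---|---|---|---|---|
| 40% | 10% | 10% | 40.6% | 0.2 |
| 30% | 10% | 10% | 30.7% | 0.2 |
| 30% | 30% | 30% | 36.3% | 1.9 |
| 30% | 50% | 50% | 47.5% | 5.3 |
| 20% | 50% | 50% | 40.0% | 6.0 |

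For the first row, 0.60 × 0.10 × 0.10 = 0.006, and 30 × 0.006 = 0.18. For the last, 0.80 × 0.50 × 0.50 = 0.20, and 30 × 0.20 = 6.0. The range is therefore about 0.6 to 20 percentage points.

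Two limits apply. If patients who have the event after new therapy tend to be those who already had it on study, the excess is smaller. And b counts every event after new therapy starts, including late effects of the study regimen, so not all of the excess is misattributed.

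**The case against.** The strongest reply is that this is a deliberate choice. Section 9.4.5 considers events after further therapy, keeps them and flags them. A fixed post-dose window regardless of cause avoids losing delayed toxicity, which matters with antibody partners. A cut at next therapy would drop some true late effects. Either table alone has a cost. This stands, and it is why the cut table should not replace the full-window one. It does not justify having only one of them.

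It can also be said that Section 9 is a summary and that a supplementary table belongs in the SAP. A SAP could add one. But the protocol itself fixes the content of the summaries, and a SAP that follows it without addition would carry the mixture forward.

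Four stronger readings are tempting, and the documents do not support them:

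- A reader might infer that next-line events also enter the causally related tables. They do so only if the investigator rates them as related to the study product. That rating is open-label and a matter of judgement, but it is a real filter.
- A reader might turn the windows into shares of observation time. Take the Phase 1 combination median PFS of 14.9 weeks (Section 2.3), about 104 days, as time on treatment. A 90-day window with new therapy at day 30 gives 60/(104 + 90) = 31%. A 30-day window with new therapy at day 14 gives 16/(104 + 30) = 12%. The start days are assumed, every patient is taken to start new therapy, and person-days are not the proportion of patients with an event. Neither figure is an inflation of an AE rate.
- A reader might infer that the two modules are affected differently. The module windows are not in the text at hand, and Section 9.2 plans no formal comparison between cohorts.
- A reader might infer that overlap is universal. Section 7.1.1 leaves standard of care to the investigator and gives no timing. Inclusion criterion 5 requires prior progression on standard-of-care therapy, and Section 4.2 speaks of patients whose options are exhausted, so some may start nothing within the window.

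**Conclusion.** The point holds for the all-cause AE tables. As written, Section 9.4.5 lets them include events that begin on next-line therapy and provides no table that separates those events. The causally related tables are largely protected.

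The size cannot be established from the protocol. Over the assumed ranges above it runs from negligible (0.2 patients) to 6 patients of 30 per module. The upper end could alter a tolerability judgement on an uncontrolled cohort; the lower end would not. The conclusion that the tables can mix the two sources rests only on the text. The numbers rest on the three assumed inputs and on independence. This is a worthwhile and inexpensive improvement to the presentation; it does not call the safety data themselves into question.

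**What to change.** In Section 9.4.5, and in the SAP to match:

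1. Present the all-cause AE summaries with events counted up to the earlier of the end of the 30- or 90-day follow-up window and the day before first subsequent anticancer therapy.
2. Tabulate separately the AEs inside the window with onset on or after the start of that therapy.
3. Keep the full-window summary alongside, including serious and immune-mediated AEs, so that delayed toxicity stays visible.

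The listing flag in 9.4.5 already requires AE onset to be compared with the start of further therapy, and Section 8.2.8.3 provides for follow-up of subsequent cancer therapy. AE collection, reporting and patient management do not change. The cost is a sentence or two of text and a few extra tables. Late-onset events after new therapy will appear only in the separate and full-window tables, so the footnotes should say so.

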9.4.6 Other analyses

The analysis of the secondary endpoints PK, known metabolites and immunogenicity will be reported in the CSR. CCI [REDACTED]

9.4.7 COVID-19 analyses

Refer to the Statistical Analysis Plan for details regarding COVID-19.

9.5 Interim analyses

No formal interim analysis is planned. CCI [REDACTED]

11 SUPPORTING DOCUMENTATION AND OPERATIONAL CONSIDERATIONS

Appendix A Regulatory, ethical and study oversight considerations

A 1 Regulatory and ethical considerations

This study will be conducted in accordance with the protocol and with the following:

- Consensus ethical principles derived from international guidelines including the Declaration of Helsinki and Council for International Organizations of Medical Sciences (CIOMS) International Ethical Guidelines
- Applicable ICH Good Clinical Practice (GCP) Guidelines
- Applicable laws and regulations

The protocol, protocol amendments, ICF, Investigator Brochure, and other relevant documents (e.g., advertisements) must be submitted to an IRB/IEC by the Investigator and reviewed and approved by the IRB/IEC before the study is initiated.

Any amendments to the protocol will require IRB/IEC approval before implementation of changes made to the study design, except for changes necessary to eliminate an immediate hazard to study patients.

The Investigator will be responsible for the following:

- Providing written summaries of the status of the study to the IRB/IEC annually or more frequently in accordance with the requirements, policies, and procedures established by the IRB/IEC
- Notifying the IRB/IEC of SAEs or other significant safety findings as required by IRB/IEC procedures
- Providing oversight of the conduct of the study at the site and adherence to requirements of 21 CFR, ICH guidelines, the IRB/IEC, European regulation 536/2014 for clinical studies (if applicable), and all other applicable local regulations

The study will be performed in accordance with the AstraZeneca policy on Bioethics and Human Biological Samples.

Regulatory Reporting Requirements for SAEs

- Prompt notification by the investigator to the sponsor of a SAE is essential so that legal obligations and ethical responsibilities towards the safety of participants and the safety of a study intervention under clinical investigation are met.
- The sponsor has a legal responsibility to notify both the local regulatory authority and other regulatory agencies about the safety of a study intervention under clinical

investigation. The sponsor will comply with country-specific regulatory requirements relating to safety reporting to the regulatory authority, IRBs, and investigators.

- For all studies except those utilizing medical devices investigator safety reports must be prepared for suspected unexpected serious adverse reactions (SUSAR) according to local regulatory requirements and sponsor policy and forwarded to investigators as necessary.
- An investigator who receives an investigator safety report describing a SAE or other specific safety information (e.g., summary or listing of SAEs) from the sponsor will review and then file it along with the Investigator's Brochure and will notify the IRB, if appropriate according to local requirements.

A 2 Financial disclosure

Investigators and sub-Investigators will provide the Sponsor with sufficient, accurate financial information as requested to allow the Sponsor to submit complete and accurate financial certification or disclosure statements to the appropriate regulatory authorities. Investigators are responsible for providing information on financial interests during the course of the study and for 1 year after completion of the study.

A 3 Informed consent process

The Investigator or his/her representative will explain the nature of the study to the patient or his/her legally authorized representative and answer all questions regarding the study.

Patients must be informed that their participation is voluntary. Patients or their legally authorized representative will be required to sign a statement of informed consent that meets the requirements of 21 CFR 50, local regulations, ICH guidelines, Health Insurance Portability and Accountability Act (HIPAA) requirements, where applicable, and the IRB/IEC or study center.

The medical record must include a statement that written informed consent was obtained before the patient was enrolled in the study and the date the written consent was obtained. The authorized person obtaining the informed consent must also sign the ICF.

Patients must be re-consented to the most current version of the ICF(s) during their participation in the study.

A copy of the ICF(s) must be provided to the patient or the patient's legally authorized representative.

CCI

If a patient's partner becomes pregnant during or within 3 months (or as indicated in module-specific appendix) after the study, the partner is asked to sign the "Adult Study ICF for Pregnant Partners of Study Patients" and provide information about the pregnancy accordingly.

The ICF will contain a separate section that addresses the use of remaining mandatory samples for optional exploratory research. The Investigator or authorized designee will explain to each patient the objectives of the exploratory research. Patients will be told that they are free to refuse to participate and may withdraw their consent at any time and for any reason during the storage period. The patient will give a separate agreement to allow any remaining specimens to be used for exploratory research. Patients who decline to participate in this optional research will indicate this in the ICF. If a patient withdraws consent to the use of donated biological samples, the samples will be disposed of/destroyed, and the action documented. If samples already have been analyzed at the time of the request, AstraZeneca will not be obliged to destroy the results of this research.

A 4 Data protection

Each patient will be assigned a unique identifier by the Sponsor. Any patient records or data sets transferred to the Sponsor will contain only the identifier; patient names or any information which would make the patient identifiable will not be transferred.

The patient must be informed that his/her personal study-related data will be used by the Sponsor in accordance with local data protection law. The level of disclosure must also be explained to the patient.

The patient must be informed that his/her medical records may be examined by Clinical Quality Assurance auditors or other authorized personnel appointed by the Sponsor, by appropriate IRB/IEC members, and by inspectors from regulatory authorities.

A 5 Committees structure

The safety of all AstraZeneca clinical studies is closely monitored on an on-going basis by AstraZeneca representatives in consultation with Patient Safety. Issues identified will be addressed; for instance this could involve amendments to the Clinical Study Protocol and letters to Investigators.

A 6 Dissemination of clinical study data

A description of this clinical trial will be available on <http://astrazenecaclinicaltrials.com> and <http://www.clinicaltrials.gov> as will the summary of the main study results when they are available. The clinical trial and/or summary of main study results may also be available on other websites according to the regulations of the countries in which the study is conducted.

A 7 Data quality assurance

All patient data relating to the study will be recorded on printed or eCRF unless transmitted to the Sponsor or designee electronically (e.g., laboratory data). The Investigator is responsible for verifying that data entries are accurate and correct by physically or electronically signing the eCRF.

The Investigator must maintain accurate documentation (source data) that supports the information entered in the eCRF.

The Investigator must permit study-related monitoring, audits, IRB/IEC review, and regulatory agency inspections and provide direct access to source data documents.

The Sponsor or designee is responsible for the data management of this study including quality checking of the data.

Study monitors will perform ongoing source data verification to confirm that data entered into the eCRF by authorized site personnel are accurate, complete, and verifiable from source documents; that the safety and rights of patients are being protected; and that the study is being conducted in accordance with the currently approved protocol and any other study agreements, ICH GCP, and all applicable regulatory requirements.

Records and documents, including signed ICFs, pertaining to the conduct of this study must be retained by the Investigator for 15 years after study completion unless local regulations or institutional policies require a longer retention period. No records may be destroyed during the retention period without the written approval of the Sponsor. No records may be transferred to another location or party without written notification to the Sponsor.

A 8 Source documents

Source documents provide evidence for the existence of the patient and substantiate the integrity of the data collected. Source documents are filed at the Investigator's site.

Data reported on the eCRF that are transcribed from source documents must be consistent with the source documents or the discrepancies must be explained. The Investigator may need to request previous medical records or transfer records, depending on the study. Also, current medical records must be available.

Definitions of what constitutes source data can be found in the clinical trial agreement.

A 9 Study and site closure

The sponsor designee reserves the right to close the study site or terminate the study at any time for any reason at the sole discretion of the sponsor. The study may be stopped if, in the

judgment of AstraZeneca, trial subjects are placed at undue risk because of clinically significant findings that:

- meet individual stopping criteria or are otherwise considered significant
- are assessed as causally related to study drug,
- are not considered to be consistent with continuation of the study

Regardless of the reason for termination, all data available for the subject at the time of discontinuation of follow-up must be recorded in the CRF. All reasons for discontinuation of treatment must be documented.

In terminating the study, the Sponsor will ensure that adequate consideration is given to the protection of the subjects' interests

Study sites will be closed upon study completion. A study site is considered closed when all required documents and study supplies have been collected and a study-site closure visit has been performed.

The investigator may initiate study-site closure at any time, provided there is reasonable cause and sufficient notice is given in advance of the intended termination.

Reasons for the early closure of a study site by the sponsor or investigator may include but are not limited to:

- Failure of the investigator to comply with the protocol, the requirements of the IRB/IEC or local health authorities, the sponsor's procedures, or GCP guidelines
- Inadequate recruitment of participants by the investigator
- Discontinuation of further study intervention development

A 10 Publication policy

The results of this study may be published or presented at scientific meetings. If this is foreseen, the Investigator agrees to submit all manuscripts or abstracts to the Sponsor before submission. This allows the Sponsor to protect proprietary information and to provide comments.

The Sponsor will comply with the requirements for publication of study results. In accordance with standard editorial and ethical practice, the Sponsor will generally support publication of multicentre studies only in their entirety and not as individual site data. In this case, a coordinating Investigator will be designated by mutual agreement.

Authorship will be determined by mutual agreement and in line with International Committee of Medical Journal Editors authorship requirements.

